## LIST OF ABBREVIATIONS

|         |   |
|---------|---|
| AE      | Adverse Event   |
| CAG     | Confidential Advisory Group   |
| CI      | Chief Investigator  |
| CRF     | Case Report Form  |
| DMC     | Data Monitoring Committee   |
| GAfREC  | Governance Arrangement for NHS Research Ethics                                |
| HRA     | Health Research Authority   |
| HTA     | Human Tissue Authority  |
| ICF     | Informed Consent Form   |
| PI      | Principal Investigator  |
| PIS     | Participant Information Sheet   |
| QA      | Quality Assurance   |
| QC      | Quality Control   |
| REC     | Research Ethics Committee   |
| SAE     | Serious Adverse Event   |
| SDV     | Source Data Verification  |
| SOP     | Standard Operating Procedure  |
| TMF     | Trial Master File   |
| nTMS    | Neuro-navigated Transcranial magnetic stimulation                             |
| SCI     | Spinal cord injury  |
| ISNCSCI | International standards for neurological classification of spinal cord injury |
| EM-SCI  | European Multicentre study about Spinal cord injury                           |
| PPI     | Public patient involvement  |

## STUDY SUMMARY

| STUDY OVERVIEW                               |  |
|--|--|
| Full title                                   | Validating neuro-navigated TMS stimulation in SCI patients: a feasibility study towards a gene therapy for SCI.   |
| Objectives                                   | 
Primary objective: Whether neuro-navigated Transcranial Magnetic Stimulation can be used as an additional outcome measure to EM-SCI assessments in a Spinal Cord Injury trial?
 
Secondary objective: Whether nTMS stimulation combined with MRI Tractography can be used as an adjunct outcome tool with EM-SCI assessments for a planned first in human SCI gene therapy trial.
  |
| Type of trial                                | Single site observational study  |
| Trial design and methods                     | Recruited patients will undergo nTMS and MRI Tractography in addition to full EM-SCI assessments. Comparisons will be made to assess the sensitivity of TMS as an outcome measure and whether it can be used as an adjunct whilst assessing SCI patients.  |
| Health condition(s) or problem(s) studied    | Chronic cervical and thoracic spinal cord injuries (greater than 6 months from injury).  |
| Target sample size                           | 20 patients  |
| Trial duration per participant:              | 1 month  |
| Main inclusion/exclusion criteria:           | 
Inclusion Criteria:
 
 
- Single traumatic event at least 6 months prior to recruitment
 
- ISNCSCI grade A, B, C or D
 
- Able to participate in EM-SCI and nTMS assessments and capable of informed consent
 
 
Exclusion Criteria:
 
 
- History of Malignancy
 
- History of other Neurological disease
 
- Pregnancy
 
- Other cord lesions or tethering
 
- Cord transaction or penetrating injury
 
 |
| Statistical methodology and analysis:        | Analysis will be performed in house using SPSS statistical software (IBM SPSS software version 28).  |
| STUDY TIMELINES                              |  |
| Study Duration/length                        | 6 months   |
| Expected Start Date                          | February 2023  |
| End of Study definition and anticipated date | 31 August 2023   |

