## 1 INTRODUCTION

This is an exciting time for translating experimental Advanced Therapies into treatments for spinal cord injury (SCI). There are currently no regenerative therapies available that target the underlying biology. Over the last 5 years we have developed a viable gene therapy approach for treating SCI in pre-clinical models. We are on the cusp of translating this therapy to first-in-human studies. We are leading a programme to establish a world-first regenerative gene therapy for traumatic SCI affecting upper limb mobility (since recovery of arm/hand function is one of the highest patient priorities). Our team will develop an innovative trial design involving neurosurgical delivery of the gene therapy into the spinal cord, followed by specialist neuro-rehabilitation.

For a clinical trial to have the best chance of success, we need to address key steps which include validation of new assessment methods for the clinical trial. Our aim is to determine whether neuro-navigated Transcranial Magnetic Stimulation (nTMS) can be used as an adjunct to standard assessments of function in SCI patients. Following two patient and public involvement events (patient focus group and feedback for project design with our rehabilitation partners), we will recruit chronic SCI subjects to carry out European Multicenter Study about SCI (EM-SCI) assessments. EM-SCI assessments are well established assessment tools for SCI patients and include the EM-SCI 'core' assessments (ISNCSCI, WISCI-III, Walk Test, SCIM 3) and EM-SCI 'additional' assessments (GRASSP, Pain score, neurophysiology). We will compare and validate nTMS with EM-SCI assessments in stable chronic SCI patients with both cervical and thoracic injuries. nTMS with combined Tractography MRI of the cortico-spinal tract (the main motor pathway of the spinal cord) will allow functional characterisation and density measurements of this tract in SCI patients.

[figure not shown]

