We have pioneered the use of Chondroitinase ABC (ChABC) for treating SCI, since the first *in vivo* demonstration that local intrathecal ChABC injections could restore sensorimotor hindlimb function to paralysed rats, to the recent development of an advanced gene therapy approach for restoring upper limb function (Figure 1). ChABC has the largest body of pre-clinical evidence supporting efficacy than any other experimental treatment for SCI and is considered a leading candidate for clinical translation, with efficacy demonstrated by many labs worldwide and in numerous species, including mice, rats, dogs and primates. We developed a vector-based gene therapy strategy for ChABC and demonstrated improved function in pre-clinical SCI contusion models. With this approach we are addressing the ambitious challenge of developing regenerative therapies that enable functional reconnection of damage nerve fibres and engage paralysed muscles. GMP grade vectors are being produced and regulatory approvals are being sought for a first-in-human clinical trial.

Key to the success of the trial is the ability to assess the functional changes in SCI patients. The EM-SCI 'core' (ISNCSCI, WISCI-III, Walk Test, SCIM) and EM-SCI 'additional' assessments (GRASSP, Pain score, neurophysiology) are validated assessment tools widely used in SCI trials. While the state of art in the field is at the cusp of a breakthrough trial, we believe an additional assessment with neuro-navigated Transcranial Magnetic Stimulation (nTMS) will improve the chance of trial success since it will have greater sensitivity to pick up subtle changes. Moreover, we can select participants with residual CST function more likely to respond to a neuroplasticity- promoting treatment. nTMS is a non-invasive method using a magnetic field to stimulate the underlying cerebral cortex. In SCI, non-navigated TMS has been used to both assess function and as an adjunct to rehabilitation to promote recovery.

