### 3 OBJECTIVES

#### 3.1 Primary Objective

Can neuro-navigated Transcranial Magnetic Stimulation be used as an additional outcome measure to EM-SCI assessments in a Spinal cord injury trial?

- Compare EM-SCI assessment with nTMS in ten chronic thoracic SCI patients
- Compare EM-SCI assessment with nTMS in ten chronic cervical SCI patients

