### 4 STUDY DESIGN

This is a pilot study in the assessment of nTMS as an adjunct tool in measuring outcome within chronic spinal cord injury patients. Initial PPI events will be performed where patients will be engaged in obtaining feedback on study design and protocol for both the pilot nTMS study and the potential subsequent Gene therapy trial. Following these events, suitable patients who meet the inclusion criteria and have displayed interest in participation will be consented for the study. Patients will then attend for a single day of assessments as follows:

1 - The International Standards for Neurological Classification of Spinal Cord Injury (ISNCSCI). The International Standards for Neurological Classification of Spinal Cord Injury (ISNCSCI) assessment protocol consists of two sensory examinations, a motor examination, and a classification framework (the impairment scale) to quantify the severity of the spinal cord injury. The grading is from A to E, with A being a complete injury with no motor or sensory function and E being normal sensory function. Patients recruited will vary between A and D to give an indication of variability in the motor response to allow comparisons between injury severity.

2 – Neurophysiology. Three standard neurophysiological measures will be registered: MEP (motor evoked potentials), SSEP (somatosensory evoked potentials) and NCV (nerve conduction velocity). MEPs and SSEPs of the tibialis and ulnar nerves quantify the status of the efferent and afferent pathways in the spinal cord. The NCV will be used to exclude peripheral nerve lesions.

3 – Functional Tests. Assessment of the walking ability of patients with movement disorders is an important outcome measure in rehabilitation. The Walking Index for Spinal Cord Injury II (WISCI II) has been validated in SCI patients, The WISCI II has an original scale that quantifies a patient's walking ability; a score of 0 indicates that a patient cannot stand and walk and the highest score of 20 is assigned if a patient can walk more than 10m without walking aids of assistance. In addition, the following two time tests will be performed: Timed Up & Go (TUG) test and 10-metre walking test (10MWT).

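### Does the mismatch between the EM-SCI battery and the assessment-day list undermine the primary comparator?

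*Protocol*

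**What the plan says.** The primary objective (section 3.1) sets nTMS against EM-SCI separately in two groups of ten. One of the two lines reads "Compare EM-SCI assessment with nTMS in ten chronic thoracic SCI patients", and the other says the same for cervical patients. The Study Summary states "Recruited patients will undergo nTMS and MRI Tractography in addition to full EM-SCI assessments".

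Section 1 lists the EM-SCI core as "assessments (ISNCSCI, WISCI-III, Walk Test, SCIM 3" and the additional part as "assessments (GRASSP, Pain score, neurophysiology". Section 2 repeats both lists and says of the battery "GRASSP, Pain score, neurophysiology) are validated assessment tools widely used in SCI trials".

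Section 4 introduces the schedule with "Patients will then attend for a single day of assessments as follows" and then gives items 1 to 6 without a gap: ISNCSCI; neurophysiology; functional tests; SCIM 3; GRASSP version 1; and MRI tractography with nTMS. No item is a Pain score. On the walking index it says "The Walking Index for Spinal Cord Injury II (WISCI II) has been validated in SCI patients". It describes GRASSP as a hand-function measure for cervical injury. It also schedules two timed walking tests, although patients of grades A to D are enrolled.

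**The concern.** The protocol asks whether nTMS can be used alongside EM-SCI and whether it is more sensitive, so what counts as EM-SCI decides what nTMS is judged against. If the battery is the full one, staff who follow section 4 will omit one component. With a single assessment day and no repeat visit, no analysis plan could recover it. Two names for the walking index also leave doubt about which instrument is meant.

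Two further points look related. The list is not restricted by injury level, so GRASSP appears to be given to thoracic patients, for whom it may say little. The timed tests appear to be given to everyone, although some of those enrolled may be unable to stand or walk. A result reported as EM-SCI against nTMS could then rest on different measures in different patients.

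**Working it through.** No power, error rate or effect size is stated, so there is no planning figure to reproduce beyond 10 + 10 = 20, which agrees with the target. The check sets the texts side by side.

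**1. Components against the list**

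| Component (sections 1 and 2) | Section 4 | Result |
|---|---|---|
| ISNCSCI | item 1 | same |
| WISCI-III | item 3, as WISCI II, scored 0 to 20 | version differs |
| Walk Test | item 3, as TUG and 10MWT | same, made specific |
| SCIM 3 (SCIM in section 2) | item 4 | same |
| GRASSP | item 5 | same |
| Pain score | none | absent |
| Neurophysiology | item 2: MEP, SSEP, NCV | same |

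Four match by name, one as specific tests, one in another version, and one is absent: 4 + 1 + 1 + 1 = 7. The list covers 7 − 1 = 6. Its numbering is unbroken, so an item lost from the text is unlikely.

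**2. Which text governs.** Sections 1 and 2 are introductory and describe the battery in general. Section 4 says what is done on the day. It also gives purposes; for example, "The NCV will be used to exclude peripheral nerve lesions", which marks that measure as a check and not a comparator. The tension over the Pain score comes from one adjective in the summary table. Staff have one list to follow.

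**3. WISCI version.** Only WISCI II is described and given a scale. WISCI-III appears as a bare label in sections 1 and 2. Following section 4 leaves no choice open.

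**4. Does the Pain score bear on the comparison?** Section 3.2 puts the value of nTMS in its sensitivity for corticospinal tract function. Section 4 argues from the functional state of that tract, and from evoked responses in patients who show no active movement on examination. These are motor claims. The measures that speak to them (ISNCSCI motor examination, MEP, walking tests, SCIM 3, GRASSP) are all on the list. Nothing in the protocol links pain to the nTMS comparison.

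**5. GRASSP.** Section 4 already gives its scope as cervical injury, and section 3.1 already separates the cervical ten from the thoracic ten. The cervical comparison therefore rests on ten patients by design. Scores from thoracic patients would at worst be uninformative.

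**6. Timed walks.** A Walk Test is part of the stated core, so scheduling one contradicts nothing. A patient who cannot stand and walk has a defined WISCI II score of 0, and ISNCSCI and SCIM 3 apply as well. Section 5.1 admits grades A to D and asks for ability to take part in the assessments; read together, these most naturally mean able to undergo the assessment day. How an absent time is analysed belongs in a statistical analysis plan. The protocol does not give the mix of grades, so the number without a time cannot be calculated.

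**The case for a change.** The best case for a change is that the choice of instruments is a protocol matter, that the label WISCI-III appears twice and so is not a single typing error, and that a measure missed on the only visit is lost for good. Aligning the wording would cost almost nothing.

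Much of this stands. The texts do disagree, and if the sponsor intended the Pain score as a comparator, section 4 would fail to collect it. What is missing is a consequence. No sentence makes pain part of the comparison with nTMS, and no composite EM-SCI score is defined that would be incomplete without it. Counting how many instruments each patient contributes does not supply the consequence either. Such counts depend on assumed scope rules and an assumed share of non-walkers, and no estimate in the protocol depends on the count.

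**Conclusion.** The concern is correct as a reading of the text but does not justify changing the plan. One of seven named components is absent from the day list and one carries a different version label. Both differences lie between summary or background text and a single operative list. Carrying out section 4 as written gives the comparison that section 3.1 asks for, in the same ten plus ten patients. The GRASSP and timed-walk points are clarifications that an analyst would make from the protocol's own descriptions.

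This rests on two assumptions: that section 4 is the schedule staff follow, and that the comparison with nTMS is about motor and corticospinal function, as sections 3.2 and 4 describe it. If the sponsor did mean pain to be compared with nTMS, the second would fail, but nothing in the protocol points that way. The wording could be aligned if the document is reopened for another reason; it is not itself a reason to amend.

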## 1 INTRODUCTION

This is an exciting time for translating experimental Advanced Therapies into treatments for spinal cord injury (SCI). There are currently no regenerative therapies available that target the underlying biology. Over the last 5 years we have developed a viable gene therapy approach for treating SCI in pre-clinical models. We are on the cusp of translating this therapy to first-in-human studies. We are leading a programme to establish a world-first regenerative gene therapy for traumatic SCI affecting upper limb mobility (since recovery of arm/hand function is one of the highest patient priorities). Our team will develop an innovative trial design involving neurosurgical delivery of the gene therapy into the spinal cord, followed by specialist neuro-rehabilitation.

For a clinical trial to have the best chance of success, we need to address key steps which include validation of new assessment methods for the clinical trial. Our aim is to determine whether neuro-navigated Transcranial Magnetic Stimulation (nTMS) can be used as an adjunct to standard assessments of function in SCI patients. Following two patient and public involvement events (patient focus group and feedback for project design with our rehabilitation partners), we will recruit chronic SCI subjects to carry out European Multicenter Study about SCI (EM-SCI) assessments. EM-SCI assessments are well established assessment tools for SCI patients and include the EM-SCI 'core' assessments (ISNCSCI, WISCI-III, Walk Test, SCIM 3) and EM-SCI 'additional' assessments (GRASSP, Pain score, neurophysiology). We will compare and validate nTMS with EM-SCI assessments in stable chronic SCI patients with both cervical and thoracic injuries. nTMS with combined Tractography MRI of the cortico-spinal tract (the main motor pathway of the spinal cord) will allow functional characterisation and density measurements of this tract in SCI patients.

[figure not shown]
## 2 BACKGROUND AND RATIONALE

Worldwide, more than 20 million people live with the devastating consequences of a traumatic SCI, with >250,000 new injuries suffered each year. Along with loss of sensory and motor function and paralysis, many patients suffer incontinence, chronic pain and depression. SCI therefore imposes severe limitations on mobility, independence, full participation in society and quality of life. SCI also has a high financial burden, with healthcare costs among the highest of any medical condition (estimated at £1.4 billion per annum in the U.K.). Current treatments rely on early surgical intervention for mechanical decompression, symptomatic relief, supportive care and rehabilitation. There are currently no adequate therapies available. SCI therefore represents a clear unmet need for which new treatment options are vital.

Most spinal cord injuries occur in the neck (cervical) region, causing upper limb paralysis. Regaining use of the hands (the ability to reach, grip, hold and pick up objects) would enable independent living, is the highest rated patient priority, and would have immense impact for reducing healthcare burden and improving quality of life. King's College Hospital has one of the

largest neurosurgical units in the United Kingdom. It provides specialist acute input for all SCI covering a catchment of over 4 million people. Over the last 5 years it has admitted and treated an average of 65 SCI patients per year, with around half of these patients with a traumatic SCI. KCH's rehabilitation partner is the world-renowned National Spinal Injuries Centre (NSIC) at Stoke Mandeville, and KCH is NSIC's largest referring centre. There is an urgent need to find novel interventions to improve outcome in SCI patients both within our large patient population at King's and also the wider SCI community.

We have pioneered the use of Chondroitinase ABC (ChABC) for treating SCI, since the first *in vivo* demonstration that local intrathecal ChABC injections could restore sensorimotor hindlimb function to paralysed rats, to the recent development of an advanced gene therapy approach for restoring upper limb function (Figure 1). ChABC has the largest body of pre-clinical evidence supporting efficacy than any other experimental treatment for SCI and is considered a leading candidate for clinical translation, with efficacy demonstrated by many labs worldwide and in numerous species, including mice, rats, dogs and primates. We developed a vector-based gene therapy strategy for ChABC and demonstrated improved function in pre-clinical SCI contusion models. With this approach we are addressing the ambitious challenge of developing regenerative therapies that enable functional reconnection of damage nerve fibres and engage paralysed muscles. GMP grade vectors are being produced and regulatory approvals are being sought for a first-in-human clinical trial.

Key to the success of the trial is the ability to assess the functional changes in SCI patients. The EM-SCI 'core' (ISNCSCI, WISCI-III, Walk Test, SCIM) and EM-SCI 'additional' assessments (GRASSP, Pain score, neurophysiology) are validated assessment tools widely used in SCI trials. While the state of art in the field is at the cusp of a breakthrough trial, we believe an additional assessment with neuro-navigated Transcranial Magnetic Stimulation (nTMS) will improve the chance of trial success since it will have greater sensitivity to pick up subtle changes. Moreover, we can select participants with residual CST function more likely to respond to a neuroplasticity- promoting treatment. nTMS is a non-invasive method using a magnetic field to stimulate the underlying cerebral cortex. In SCI, non-navigated TMS has been used to both assess function and as an adjunct to rehabilitation to promote recovery.

nTMS allows for an individual location of the magnetic stimulation within an acceptable margin of error derived from the registration process. When compared with non-navigated TMS, the navigated TMS allows for more spatially discrete cortical stimulation and more stable motor evoked potentials with significantly higher amplitudes and shorter latencies. Also, when different navigation methods are compared, 'E-field' navigation proved to be superior to line-navigation method. At King's, we use an E-Field nTMS. We combine nTMS with MRI tractography, a 3D modelling technique used to visually represent nerve tracts using data collected by diffusion MRI. This accurately delineates the location of the motor cortex. The advantage for this is pairing a positive TMS cortical response with a defined subcortical tract that carries that same motor information, thus confirming a true positive response.

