4 - Spinal Cord Independence Measure 3 (SCIM 3). The Spinal Cord Independence Measure (SCIM) is a disability scale developed specifically for patients with spinal cord lesions. It focuses on the requirement of personal assistance and/or technical aids with domains in self-care, respiration and sphincter management and mobility. The score is between 0 and 100.

[figure not shown]
5 - Graded and Redefined Assessment of Strength, Sensibility and Prehension version 1 (GRASSP v1). The GRASSP is an outcome measure to assess hand function in patients with a cervical spinal cord injury. It consists of three domains: 1. Strength, 2. Sensation and 3. Prehension: including relevant finger positioning performance with 6 Activities of Daily Living. The score is between 0 and 116.

6 - MRI Tractography followed by neuro-navigated Transcranial Magnetic Stimulation will be undertaken. The rationale is that nTMS will provide a more sensitive characterisation of a functional CST in SCI patients. Moreover, nTMS provides spatial resolution of the tracts which standard neurophysiology cannot determine. The addition of MRI tractography allows accurate neuro-navigated localisation of the CST and quantification of the fibre density of the CST.

After acquisition of the MRI scans, nTMS-seeded tractography will be performed. nTMS positive motor responses will be used as regions of interest and another region of interest will be placed in the brainstem at the level of the superior cerebellar peduncle. This technique will provide somatotopic tractography. DTI-derived metrics (Fractional Anisotropy (FA), Axial Diffusivity (AD), Radial Diffusivity (RD), Mean Diffusivity (MD) and Hindrance Modulated Orientation Anisotropy (HMOA)), number of fibres and volume will be calculated for both CSTs. Our hypothesis is that an abnormal cortical excitability will correlate with abnormal CST metrics supporting microstructure impairment. This may be particularly true with the tract specific metric, HMOA.

Comparisons between EM-SCI and nTMS/tractography assessments will be made to determine if nTMS can be used as an adjunct which is more sensitive in the assessment of SCI patients. For instance, nTMS can induce motor evoked potentials in patients with no active movement detected in neurological examination and this can have an impact in terms of prognostication of motor recovery, which is especially important for SCI trials.

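### Does seeding the tract from the nTMS response undermine the claim that tractography confirms a true positive?

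*Protocol*

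**What the plan says.** The last paragraph of Section 2 describes combining nTMS with diffusion tractography. It first states what the combination delivers: "This accurately delineates the location of the motor cortex". It then gives the advantage as "pairing a positive TMS cortical response with a defined subcortical tract that carries that same motor information, thus confirming a true positive response".

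The procedure is in Section 4, item 6. For the seed, "nTMS positive motor responses will be used as regions of interest". For the other end, "another region of interest will be placed in the brainstem at the level of the superior cerebellar peduncle". No further region is named. Item 6 says that adding tractography "allows accurate neuro-navigated localisation of the CST and quantification of the fibre density of the CST", and it lists diffusion metrics, fibre number and volume for the tracts on both sides. Section 1 says the combination "will allow functional characterisation and density measurements of this tract in SCI patients".

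Item 6 ends with the comparison against EM-SCI, which is meant to "determine if nTMS can be used as an adjunct which is more sensitive in the assessment of SCI patients". Its example is that "nTMS can induce motor evoked potentials in patients with no active movement detected in neurological examination".

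The Study Summary gives the injuries as cervical and thoracic, and Section 3.1 plans ten patients of each kind.

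**The concern.** There are two grounds for unease.

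- **Independence.** The tract is sought where nTMS has already been positive. A check that starts from the result under test is not a separate reference standard, and item 6 describes no tract from nTMS-negative sites for comparison.
- **Level.** The tract is defined between cortex and upper brainstem, while the injury is in the cord below. A patient could have an intact intracranial pathway whether or not anything conducts through the lesion.

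The stake would be the claim of greater sensitivity. Extra nTMS positives in patients without active movement count as added sensitivity only if they are real. If a tract between cortex and brainstem were taken as proof that they are real, that claim would rest partly on a check unable to test it. The secondary objective, which looks to nTMS for selecting and stratifying patients in later trials, would inherit the weakness. A smaller point is that Sections 1 and 4 speak of corticospinal tract density without naming the segment, so a reader could take it to mean the injured cord.

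**Working it through.** The protocol gives no figure for this point, so the check sets the sections side by side.

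**1. Where the tract lies.** Item 6 names two regions of interest: the nTMS-positive cortical sites and the brainstem. Section 3.1 gives 10 thoracic + 10 cervical = 20 patients. Both regions (2 of 2) are above the lesion in all 20. The anatomical premise of the concern is correct.

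**2. What a tract says about crossing the lesion.** Let LR be the probability of finding the tract if the response crossed the lesion, divided by the probability of finding it if it did not. Posterior odds = LR × prior odds. Assume that both probabilities equal some common value p, because the segment lies above the injury. Then LR = p/p = 1 for any p above zero, and the odds do not move. The equality is an assumption. Item 6 itself hypothesises that abnormal excitability goes with abnormal tract metrics, so LR might differ somewhat from 1. Either way, a tract found between these two regions is not confirmation of conduction through the cord.

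**3. What a tract says about cortical localisation.** Diffusion MRI is a separate measurement from the muscle response, and a seed can fail to connect. Asking whether a given cortical site projects into the descending motor pathway requires starting from that site. For this question the seeding is the method itself, and the answer carries information.

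**4. Which question Section 2 is answering.** The sentence before the disputed one is about locating motor cortex. The disputed sentence refers back to it and speaks of a cortical response and a subcortical tract. It mentions neither the cord nor the lesion. The natural meaning of *true positive* there is a correctly located motor site, which is the question in step 3.

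**5. Whether any planned comparison uses the tract as a referee.**

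| Place | Planned use | Tract used to verify nTMS positives? |
|---|---|---|
| Section 3.1 | nTMS against EM-SCI | No |
| Section 3.2 | nTMS with tractography as an adjunct to EM-SCI | Not stated |
| Section 4, item 6 | Localising the tract and measuring fibre density | No |
| Section 4, item 6 | Correlating excitability with tract metrics | No |
| Section 4, item 6 | EM-SCI against nTMS/tractography, with the example of responses without movement | Not stated; in the example the evidence is the evoked potential |

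One could draw a two-by-two table of nTMS result by tract found and observe that seeding only at positive sites leaves 4 − 2 = 2 cells without data. That would rule out sensitivity, specificity and chance-corrected agreement of nTMS against the tract. The protocol proposes none of these, so the empty cells cost it nothing.

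**6. The density wording.** As described, the metrics belong to the segment from cortex to brainstem. Scan coverage is not stated, so data from the cord are not ruled out. The excitability hypothesis can be examined on the intracranial segment in either case.

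**The case for a change.** The strongest case for a change is that Section 2 states no limit on its claim, and that the tract pairing is the only confirmation of a positive response that the protocol describes. The same section also looks forward to selecting participants with residual corticospinal function, and for that purpose conduction through the injured cord is what matters. A reader moving from there to the example in item 6 could join the two and treat an intracranial connection as support for a response below the injury. Tightening the wording would need no scan or visit.

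Part of this stands. The verb is strong, the sentence could say outright that it concerns localisation, and the segment could be named wherever tract density is mentioned.

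The rest depends on a step that the protocol does not take. The harm arises only if the tract is used to verify discordant positives, and neither the objectives nor item 6 says that it will be. A rule that only responses from muscles supplied below the lesion count as evidence of residual function would be a responder definition. That is separate from the tractography claim and is commonly left to a statistical analysis plan. The example in item 6 already points analysts that way, since it concerns evoked potentials where examination finds no movement.

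**Conclusion.** The anatomical observation is correct: with its ends at cortex and brainstem, the tract cannot confirm that a response crossed a cervical or thoracic injury. It does not expose an error in the plan. The disputed sentence is background, its context limits it to cortical localisation, and the seeded tract does inform that question.

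The effect on results is nil. The primary comparison does not involve the tract, the correlation hypothesis can be examined on the segment described, and no estimate, test or sample size depends on how the sentence is read. What remains is a point of clarity about the meaning of *true positive* and the segment to which the density figures refer, which authors would ordinarily settle when reporting.

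This rests on two assumptions: that Section 2 is read with its preceding sentence, and that no analysis plan makes finding a tract a condition for counting an nTMS response as evidence of conduction across the lesion. If one did, the concern would become substantive.
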